ClinicalTrials.gov NCT04491175

SPIRIT Table: eProtocol M-Stim for LBP Opioid & Pain Reduction

| Administrative | Description |
|-----------------------|---|
| Title | Multimodal Mechanical Stimulation to Reduce Opioids for Low Back Pain: A Randomized Clinical Trial An Outpatient, Double-blinded Randomized Trial Comparing the Impact of DuoTherm™ Mechanical Stimulation (M-Stim) Versus TENS on Opioid Prescribing and Use for Low Back Pain |
| Trial Registration | ClinicalTrials.gov NCT04491175 |
| Protocol Version | NIH funded protocol submitted 5/29/2019 to FDA Q191165 |
| | IRB Protocol Submission Date: 8/10/2019 |
| | Protocol Amendment Number: 4 |
| | Authors: [name] |
| | Revision Chronology: |
| | 8/10/2019 Original [COVID delay] 4/21/2022 FDA recommended modifications from Q191165 incorporated to protocol: increased sample size to 60 opioid naïve acute (for 3 months) and 100 chronic (with 6 months followup); Replaced Sham with LG Smart TENS and added a blinding assessment; Outcome measures of PROMIS Pain Interference, Pain Intensity, Depression to be measured weekly the first month. 6/8/2022 – Final survey design reduced daily diary reporting to 1 month due to budget constraints of longer follow up. Depression and Catastrophizing only as baseline; weekly NRS Pain Interference (3) PROMIS Pain Interference (2) and Pain Intensity collected until 3 months for all; Monthly surveys added past month NRS, Blinding assessment to monthly survey at 3 months and after for those started in chronic strata. Added "source" for each opioid use case to DOSE tool collecting opioid formulation, dose, and number of pills. 5/5/23; Added "Do you think you will need surgery" and "do you |
| | think you will need epidural" questions, and "did you get surgery" and "did you get an epidural" to monthly. |
| | 5) 7/13/2023 New Location added |

| Funding | National Institute on Drug Abuse, R44DA049631, R44DA058952 |
|--|---|
| Roles and Responsibilities | Principal Investigator: [name] MD, responsible for study design, overall project oversight, and compliance. Study Coordinator: [name], responsible for daily operation, protocol adherence and patient coordination at Kaizo Health Centers. [name] assisted [name] with initial study design, ongoing recruitment recommendations, pain measure decision-making, study flow creation. [name] PhD (Deceased), responsible for initial power analysis, statistical support for study design, revisions after FDA. [name] PhD, responsible for programming of data collection instruments, ongoing support of data collection tool and dataset, database consolidation; [name] PhD, responsible for statistical analysis of completed dataset. All apart from [name] reviewed the manuscript. |
| Introduction | Low back pain (LBP) affects nearly 40% of adults, contributing to significant reductions in quality of life and productivity. The opioid epidemic, largely driven by prescriptions for pain, has created an urgent need for effective non-pharmacological pain treatments. Existing options such as TENS devices may provide acute relief, but are not available as an opioid substitute. A multimodal approach, combining mechanical stimulation, heat, cold, and acupressure, holds promise for reducing both acute and chronic pain and opioid prescribing. |
| Background and rationale for the study | Between 25 and 50% of patients presenting with acute or exacerbated chronic LBP (a/cLBP) receive prescriptions for opioids. ALBP progresses to chronic in 40% of those with moderate to severe pain (4 out of 10 on a 0 – 10 Numeric Rating Scale). Opioid pain relief is no better than placebo at 6 weeks after presentation, but increases the risk of cLBP and persistent use (5% of opioid naïve). Providing a multimodal low back pain device could reduce opioid prescribing or use compared to TENS; providing any device could reduce opioid prescribing and use compared to contemporaneous prescribing practices. |
| Objectives | Primary Objective, Opioids: To determine whether the use of a multimodal neuromodulatory mechanical stimulation (M-Stim) device (DuoTherm) can reduce opioids 30% compared to TENS in those with moderate to severe back pain. |

| Study Design | Co-Primary Objective, Acute Pain: To determine whether multimodal M-Stim reduces Pain Intensity 30% more than TENS in the first 10 days after presenting for treatment. Co-Primary Objective, Chronic Pain: To determine whether multimodal M-Stim reduces disability 30% more than TENS at 6 months. A randomized, double-blind controlled trial with 3- (aLBP) or 6- month (cLBP) follow-up. |
|-------------------------|--|
| Study Setting | The study will be conducted at mixed physical therapy/chiropractic practices in Washington, DC, Maryland, and Virginia, which offer demographic and economic diversity. These clinics provide an ideal environment, with frequent follow-ups and ongoing therapy but no onsite access to opioid prescribers. |
| Eligibility Criteria | Inclusion Criteria: - Male or female adults aged 18-90 presenting for treatment of acute or chronic low back pain - Self report of moderate to severe LBP of 4 or greater out of 10 on a 0-10 Numeric Rating Scale. - Acute: pain duration <3 months not using opioids for the current exacerbation of low back pain - Chronic: Pain duration >= 3 months with or without ongoing opioid use - Capacity to understand risks and benefits (informed consent). - Smartphone for Qualtrics web-based platform use Exclusion Criteria: - Radicular pain likely reflecting a surgical or mechanical problem - Inability to apply or use the device - Sensitivity to cold or vibration (e.g Raynaud's or Sickle Cell Disease) - Diabetic neuropathy rendering a patient unable to determine if the device is too hot - New neurologic deficits, skin lesions over the low back area - A contraindication to any medication for pain management that would impact analgesic use record |

| | - Pacemaker |
|--------------|---|
| Intervention | The experimental arm DuoTherm is a novel multimodal low back pain relief device incorporating 8 harmonic vibration patterns of mechanical stimulation (M-Stim) including neuromodulatory frequencies, 5 intensity levels, and optional heat, cold, and pressure delivered through a sculpted metal plate attached with a belt and controlled by buttons on the belt. Patients will be instructed to use the device at least daily for 30 minutes. The active control is a prescription 4-lead 8-channel TENS unit (LG Smart) with variable intensity. |
| | Participants will be instructed to use the device for a minimum of 30 minutes a day. Both M-Stim and LG Smart TENS groups will receive a standard pain management regimen typically used for low back pain standardized across all clinicians participating in the study. Participants will keep the devices and be instructed to use them for pain as needed during the duration of the study. |
| Outcomes | Opioid Use Primary Outcome: |
| | Prior use: For patients with prior or ongoing opioid use, a 30% reduction in MME (Milligram Morphine Equivalents) between the first 14 days and the last 14 days of daily diary recordings using the DOSE data collection tool. |
| | Opioid naïve: 30% reduction of those receiving an opioid prescription "prescribed to me for this event" |
| | Secondary outcomes: Use days; total MME and use past 7 days in the opioid naïve; use days by those with more severe pain using the NIH Research Taskforce definitions; and prescribing compared to a contemporaneous national LBP population (25%). |
| | Pain Primary Outcome: |
| | Chronic: 30% lower disability at 6 months using PROMIS Pain Interference for those with ongoing pain >3 months |
| | Acute: 30% lower NRS 0-10 "pain now" from entry to 10 days for those presenting with an episode of pain starting within the past 2 weeks |
| | Secondary Outcomes: Change in disability for those with >=57.7 PROMIS Pain Interference; restoration of function to normal (PI=50); |

| | integrated analysis with | n common | criteria fo | r restoration | on of function | on with | |
|-------------------------|---|---------------|--------------------|---------------------|----------------------|----------------------------|--|
| | multifidus stimulation s | surgery. | | | | | |
| | | | | | | | |
| Participant Timeline | | Initial Visit | Daily x 28 days | Weekly for 3 months | Monthly for 3 months | Monthly 4 - 6 months | |
| | Consent, Enrollment, Randomization | ALBP, CLBP | | | | | |
| | Minimum Dataset, Pain Catastrophizing Sullivan, PROMIS Depression, Physical Function | ALBP, CLBP | | | | | |
| | NRS (at that moment & past 24 hours) | ALBP, CLBP | ALBP, CLBP | ALBP, CLBP | ALBP, CLBP | CLBP | |
| | NRS after 30 minutes | ALBP, CLBP | | | | | |
| | NRS Past week | | | ALBP, CLBP | ALBP, CLBP | CLBP | |
| | NRS Past month | | | | ALBP, CLBP | CLBP | |
| | PROMIS Pain Intensity, Pain Interference | ALBP, CLBP | | ALBP, CLBP | ALBP, CLBP | CLBP | |
| | Dose, Opioid formulation, number Source (DOSE tool), other analgesics | ALBP, CLBP | ALBP, CLBP | ALBP, CLBP | ALBP, CLBP | CLBP | |
| | Device usage | | ALBP, CLBP | ALBP, CLBP | ALBP, CLBP | CLBP | |
| Sample Size | To estimate the M-Stim | interventi | on effect : | size, a retro | spective st | udy of | |
| | 59 cLBP patients on ch | ronic opioi | ds (100% | prolonged | opioid use) | | |
| | reported a 28% reducti | on in MME | after spin | al stimulat | or | | |
| | implantation,[40] reducing MME 26.2(SD32.8) compared to 5.8(SD34.2) | | | | | | |
| | for those with conventional treatment (effect size 0.60. A priori, we would | | | | | | |
| | be able to detect an effect size of 1 (meaning a difference of 1 standard | | | | | | |
| | deviation) with 94% power and alpha of .03 using a Wilcoxon Mann | | | | | | |
| | Whitney test with 30 in each group. With this effect size for a two-sided | | | | | | |
| | significance of 0.05, 17 participants per group would detect a 30% | | | | | | |
| | prescribing reduction, while 50 participants on chronic opioids per | | | | | | |
| | treatment group would provide 85.4% power to detect a 30% reduction in | | | | | | |
| | MME. Given the 20% in a previous study by Jamieson et al, we increased | | | | | | |
| | the cLBP sample to 50 | - | | Jannoson | icat, we iiio | ioasea | |
| | | | | | | | |

| | We planned to recruit 60 aLBP participants who had never taken opioids for their back pain, and 100 cLBP without a new prescription but with or without chronic opioid for cLBP. |
|----------------------------|--|
| Recruitment | Patients were recruited from Kaizo Health Centers in Landover and Fairfax, through direct referrals, flyers, and digital content like social posts and emails targeting local populations. Flyers were also distributed at three local pain clinics. |
| Randomization | After eligibility screening and informed consent, a 4-digit participant ID and the intervention allocation were randomly assigned by the survey software to either the DuoTherm or LG Smart TENS group within acute and chronic arms. A copy of the informed consent was emailed to the participant. |
| Blinding (masking) | Participants were blinded to which device powered the study hypothesis, and blinded to their assigned intervention until after documenting initial NRS pain intensity. Success of blinding the study device (M-Stim) versus the active control (TENS) was tested at months 3-6 with prompts, "select which group you think you were in (control or treatment)" and "How confident are you (0 = Least Confident 100 = Most Confident)." The protocol statistician and study coordinator knew the intervention assignments during enrollment but did not conduct statistical analysis. The PI and treating chiropractor were blinded to allocation during enrollment, with the PI accessing data only after study completion. The analyzing statistician was blinded to device assignment until completion of data cleaning and initial analysis. |
| Data Collection Methods | Site coordinators entered identification and contact information after informed consent on a tablet, then recorded weight, height, and duration to confirm acute or chronic follow-up duration, then participants took the tablet to record pain intensity on a 0-10 NRS now and past 24 hours. While using the device for 30 minutes, participants completed 7-day pain intensity NRS, NIH Back Pain Research Minimum Dataset, including PROMIS measures of Physical Function, Pain Interference, Depression, and Catastrophizing via the Sullivan Catastrophizing scale, Injury Mechanism, prior treatments, exercise and athletic status. |
| | Participants were prompted to record analgesic use, pain, and device use daily for a month on the web-based platform, then weekly, with the monthly surveys adding Pain Interference. All surveys asked about |

analgesic use. Due to the anticipated heterogeneity of opioid formulations, a skip-logic data collection instrument algorithm was created with robust options for Dose per pill (34), Opioid formulations, e.g. hydrocodone, hydromorphone etc. (15) and the Source (DOSE tool, Supplement 2). Sources included "prescribed to me for this event", "prescribed to me for another event", "given to me by a family member", "given to me by a friend", "given to me by an acquaintance or stranger", or "purchased from someone without a prescription". These were converted to a total milligram morphine equivalent (MME) for analysis.

Participants recorded when they used their device, duration of use, and any additional pain relief modalities (exercise, stretching, bath, hot tub, therapy, massage). Patients were asked to record any thermal use or therapy cycle or channel as appropriate to their device.

Participants verbally endorsing pain for less than three months (acute) were entered into a 3 month follow-up program, or 6 months (chronic) for those for whom back pain had been an ongoing problem for more than 3 months.

Statistical Methods

Statistical analysis was performed with masked intervention allocation by a statistician new to the project to determine differences in primary and secondary outcomes.

An intention-to-treat analysis included all participants meeting inclusion criteria. Summary statistics (means, standard deviations, proportions) were calculated using T-tests and Chi-squared tests. Opioid prescribing differences were calculated with raw percent of change and relative risks. Diary entries and item-level data were analyzed for missing data to assess the need for imputation. Relative risks were calculated for MME and opioid use days between intervention groups, with paired T-tests used to compare first two and last two weeks of MME in those who used opioids during the study. A linear regression assessed BMI's interaction with opioid use, calculating marginal effects with standard errors via the Delta Method. Data analysis was performed using STATANow/SE 18.5.

For pain outcomes, in addition to the above methods, missing 10 day NRS-1 data will be imputed using forward fill and KNN. A neural network will be created to determine factors contributing to 13 week Pain Interference, with iterative modeling to reduce mean absolute error. Graphs with r-squared for predictors will be generated.

| Data Monitoring | Data collection was conducted through an app that tracked daily pain, opioid use and device usage. Monitoring included weekly enrollment review by the protocol statistician to assess comprehension of the data collection tool. Adverse events were reported as per protocol. | |
|------------------------|---|--|
| | Obtained data was stored on password-protected network drives made accessible solely to the listed investigators. Data analysis will only be conducted in secure rooms with restricted access. These rooms will only be accessible to investigators. Patient samples will not be obtained. The Institutional Review Board reserves the right to audit any research files to assure the quality of any data used in this research | |
| Safety/Harm | Q191165/S001 FDA ruled Non-significant Risk 18-Sept 2019. Risks are minimal, similar to those associated with a handheld massager or standard heat/cold therapy. Patients will be screened for sensitivity to cold or vibration. Any significant adverse events will be reported to the IRB and NIH within 24 hours. Device-related adverse events will be documented and reported. | |
| Auditing | Periodic auditing will be conducted by the Institutional Review Board (IRB) to ensure compliance with protocol and safety regulations, and by site visits by the PI. | |
| Ethics Approval | This trial has received ethics approval from the Kaizo Clinical Research Institute IRB and is registered under NCT04491175. | |
| Protocol Amendments | Revision Chronology: 1) 8/10/2019 Original [COVID delay] | |
| | 4/21/2022 Incorporated FDA recommended modifications from Q191165 incorporated to protocol: increased sample size to 60 opioid naïve acute and 100 chronic (with 6 months followup); Replaced Sham with LG Smart TENS active control with 8 preprogrammed patterns to correspond with 8 preset DuoTherm therapy cycles and added blinding assessment. Outcome measures of PROMIS Pain Interference, Pain Intensity, Depression to be measured weekly the first month. We extended the follow-up from one week for acute pain to 3 months for acute pain and 6 months for chronic pain. 6/8/2022 – Final survey design reduced daily diary reporting to 1 month due to budget constraints of longer follow-up. Depression | |
| | and Catastrophizing only as baseline; weekly NRS Pain Interference (3) PROMIS Pain Interference (2) and Pain Intensity collected until 3 months for all; "Past month NRS" added to | |

monthly surveys added past month NRS, Blinding assessment for additional 3 months for those started in chronic strata. Added "source" for each opioid use case to DOSE tool collecting opioid formulation, dose, and number of pills. We intended to use evaluate change in MME over time for chronic opioid users. The FDA recommended requiring participants on opioids maintain dosage and frequency. As we did not have access to prescribing records, and opioid reduction was a desired outcome measure, we evaluated opioid use for the first two weeks versus the last two of those endorsing prior opioid use. We extended the baseline and follow-up Pain Intensity measurements to one month rather than one week. 3a) 8/31/22 – Site Visit. PI noted staff using "will not fit" criteria rather than BMI of 30 from pilot study. New device fits variable BMI, based on abdominal girth. Retained "if device fits", exclusion criteria using BMI changed to BMI >50, noting controversy in using BMI as exclusion criteria. 4) 5/5/23; Added "Do you think you will need surgery" and "do you think you will need epidural" questions, and "did you get surgery" and "did you get an epidural" to monthly. 5) 7/13/2023 New Location added Stratification by chronicity versus opioid use status: enrollment strata were based on verbal endorsement of duration and no acute opioid use for back pain. Initial evaluation of registration data after enrollment was complete revealed 16 of 60 in the "acute" strata reported a duration longer than three months, and half in each chronicity strata no prior opioids for LBP. In consultation with Clinical Trials.gov, we pooled the data and included both opioid and pain outcomes as a single NCT04491175 registry with two different publications and analyses. Informed Informed consent will be obtained from each participant after screening. Consent Participants will be informed about the voluntary nature of the study, with a HIPAA form for confidentiality. Consent will be documented via selecting 'continue' on the digital consent form. Confidentiality Patient data will be stored on password-protected network drives. All data will be de-identified using a unique study ID for each participant. Confidential records will be stored in secure, restricted-access rooms. Declaration of The principal investigator has financial conflict of interest from design interests and research into the DuoTherm device, and creating a company to

| | develop the device with NIH SBIR funding. The collaborators declare no financial or personal conflicts of interest related to this study. |
|------------------|---|
| Dissemination | Results will be disseminated through peer-reviewed journals, |
| Policy | conferences, and possibly through NIH publications, ensuring that both positive and negative outcomes are reported. |
| Ancillary and | Patients will receive standard care post-trial and may keep their devices |
| Post-Trial Care | if found beneficial. Participants will be provided referrals for ongoing care as needed. |
| Publication Plan | High impact journal, with presentation at the IASP or similar pain-related |

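### Acute co-primary: the day-10 pain comparison has no stated adjustment for the entry rating; adjust for it, and report the 10-day mean as supportive

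*Combined protocol and SAP*

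**What the plan says.** The acute co-primary objective (Objectives and Study Design) is "To determine whether multimodal M-Stim reduces Pain Intensity 30% more than TENS in the first 10 days after presenting for treatment". The Pain Primary Outcome for acute pain (Outcomes) is a 30% lower momentary NRS "from entry to 10 days for those presenting with an episode of pain", limited to episodes that began in the two weeks before presentation.

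The Participant Timeline schedules momentary and past-24-hour NRS at the initial visit and daily for 28 days. Data Collection Methods agrees: "Participants were prompted to record analgesic use, pain, and device use daily for a month on the web-based platform". The entry NRS is recorded before the 30-minute device session, and Blinding (masking) says that participants did not know their device until that rating was documented.

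Statistical Methods names t-tests and chi-squared tests and applies them to the pain outcomes as well. The other named methods serve opioid outcomes (relative risks, paired t-tests on MME, a regression on BMI) or 13-week Pain Interference (a neural network). For the acute outcome it adds only that "missing 10 day NRS-1 data will be imputed using forward fill and KNN". The label NRS-1 is not defined. No covariate, 10-day average, area under the curve or repeated-measures model is named.

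**The concern.** Read together, these sections point to one day-10 value per participant, compared between arms by t-test. Three things are left open: whether the variable is the day-10 score or its change from entry, whether the entry rating is used at all, and what the daily ratings before day 10 contribute. The objective's phrase about the first 10 days adds a further possible reading, the course of pain over the period.

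This is a co-primary endpoint in a small group. Sample Size plans 60 acute participants, which is 30 per arm if allocation is equal (the ratio is not stated). Two analysts could follow the text and report different estimates. With so few participants, an unadjusted comparison gives up precision that data already on the schedule could supply.

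**Working it through.** **The plan's own figure.** Sample Size states 94% power for a 1 SD difference, 30 per group, alpha 0.03, Wilcoxon-Mann-Whitney. The normal approximation gives 95.6%, or 94.7% with the test's relative efficiency of 0.955. A simulation of 20,000 trials gives 93.7%. The figure reproduces, but it is not tied to the NRS. The documents give no SD, correlation or power for acute pain.

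**Inputs.** n = 30 per arm, from 60 acute participants with equal allocation assumed. Assumed because the documents are silent: SD 1 at each time (standardised), entry-to-day-10 correlation r, and an illustrative day-10 effect of 0.6 SD.

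**Residual variance of three day-10 analyses.**
- Unadjusted day-10 score: 1
- Change from entry: 2(1 − r)
- Day-10 score adjusted for entry (ANCOVA): 1 − r²
- ANCOVA relative to change: (1 − r²) / [2(1 − r)] = (1 + r)/2

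Power is Φ(0.6/√(2v/30) − 1.96), two-sided 0.05. For v = 1 this is Φ(2.324 − 1.96) = 64%.

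| r | Change variance | ANCOVA variance | ANCOVA / change | Power: unadjusted | Power: change | Power: ANCOVA |
|---|---|---|---|---|---|---|
| 0.4 | 1.20 | 0.84 | 0.70 | 64% | 56% | 72% |
| 0.6 | 0.80 | 0.64 | 0.80 | 64% | 74% | 83% |
| 0.7 | 0.60 | 0.51 | 0.85 | 64% | 85% | 90% |
| 0.8 | 0.40 | 0.36 | 0.90 | 64% | 96% | 97% |

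The relevant r spans ten days, not one. If correlation decays day by day, even 0.9 between adjacent days gives 0.9¹⁰ = 0.35 from entry to day 10, and ANCOVA then leaves 1 − 0.35² = 88% of the unadjusted variance.

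**Ten-day mean.** With equal correlation r between all days, the mean of ten ratings has variance r + (1 − r)/10, or r + (1 − r)/10 − r² after adjustment for entry. A constant effect stays at 0.6 SD. An effect that builds linearly to 0.6 SD at day 10 averages 0.6 × (1 + 2 + … + 10)/100 = 0.6 × 0.55 = 0.33 SD.

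| r | Unadjusted: day 10 | Mean, constant effect | Mean, linear build-up | Adjusted: day 10 | Mean, constant effect | Mean, linear build-up |
|---|---|---|---|---|---|---|
| 0.6 | 64% | 83% | 36% | 83% | 99% | 68% |
| 0.7 | 64% | 78% | 32% | 90% | >99% | 74% |
| 0.8 | 64% | 73% | 29% | 97% | >99% | 85% |

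Across these correlations, with or without the covariate, the mean beats day 10 when the effect is constant and loses when it builds up.

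**The case against.** The strongest reply is that the objective and the outcome may be the same quantity. A reduction achieved in the first 10 days can mean the change from entry to day 10. No section says that a single rating is used, and none says that pain is averaged. That stands: a reader might infer a definite mismatch, but the documents show only loose wording.

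Three other stronger readings also fail.
- A reader might infer that a missed day-10 diary removes the participant. Statistical Methods imputes that value. Forward fill can be criticised when pain may be resolving, but the participant stays in.
- A reader might infer that nine days of ratings are discarded. Forward fill can bring an earlier rating into the endpoint, and the plan does not say what else is done with those days.
- A reader might take Pain Intensity in the objective to be the PROMIS measure. The outcome names the 0-10 NRS, and the PROMIS measure has no daily schedule, so the instrument is settled.

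It can also be said that day-10 pain is a legitimate endpoint and that replacing it with a 10-day mean is a preference. That stands too, given the trade-off above.

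Finally, the entry NRS may predict day 10 only weakly. Eligibility requires a rating of at least 4, which narrows its range, and acute pain may resolve quickly. That limits the size of the gain but does not make adjustment harmful beyond the loss of one degree of freedom.

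**Conclusion.** The concern holds as one of specification and efficiency. The acute co-primary is most naturally a day-10 t-test without baseline adjustment, and adjusting for the pre-device entry NRS improves on that whether the unadjusted variable is the score or the change. With r from 0.6 to 0.8, ANCOVA leaves 64% to 36% of the variance of the day-10 comparison and 80% to 90% of that of the change score. With r near 0.35, the gain over the unadjusted score shrinks to about 12%.

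These figures assume observed rather than imputed day-10 values. The comparison with the change score also assumes equal variances. If the 30% criterion was meant as a responder proportion tested by chi-squared, which the text does not say, they do not apply.

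The variance ratios do not depend on the sample size, but the power figures do, and 30 per arm is uncertain. The outcome is "for those presenting with an episode of pain starting within the past 2 weeks", while the stratum is defined as "Acute: pain duration <3 months not using opioids for the current exacerbation of low back pain". Protocol Amendments reports that 16 of the 60 had a longer duration than three months and that the data were pooled, so the evaluable number is unknown.

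The documents do not support making the 10-day mean the co-primary on grounds of power: the direction of the difference depends on how the effect develops, which they do not address.

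**What to change.** 1. State the acute co-primary as the momentary NRS at day 10, compared between arms by linear regression with the pre-device entry NRS as covariate. Specify the rating taken before the device session, because the timeline also has an NRS after 30 minutes of use. Report the adjusted difference with its confidence interval, and say how the 30% criterion is judged against it.
2. Add, as a supportive analysis, each participant's mean daily NRS over days 1-10 with the same covariate. Name the item averaged and the rule for missed days, consistent with the planned imputation.
3. Reword the objective so that it names the NRS and day 10.
4. Date the change. If the pain data have already been unblinded, label the adjusted analysis as added afterwards and show the unadjusted result beside it.

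The cost is a revision of the analysis text and one degree of freedom. No new data are needed: the entry rating and daily diary are already scheduled, although diary completion is not reported. Because Protocol Amendments says that enrolment is complete, the date and label are a necessary part of the change.

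### The prior-use opioid primary takes its baseline from the first 14 days on the device, so any part of the effect already present in those days is subtracted out

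*Combined protocol and SAP*

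**What the plan says.** The Outcomes section defines the prior-use opioid primary as "a 30% reduction in MME (Milligram Morphine Equivalents) between the first 14 days and the last 14 days of daily diary recordings". The Participant Timeline gives the diary as "Daily x 28 days", so the two windows are days 1-14 and days 15-28. Protocol Amendments repeats the contrast: "we evaluated opioid use for the first two weeks versus the last two of those endorsing prior opioid use". Statistical Methods names its test, "with paired T-tests used to compare first two and last two weeks of MME in those who used opioids during the study", and separately lists relative risks for MME and opioid use days between the arms.

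On timing, the Participant Timeline puts consent, enrolment and randomisation at the initial visit. Data Collection Methods has the device in use at that same visit: "While using the device for 30 minutes, participants completed 7-day pain intensity NRS". The Intervention section then says "Patients will be instructed to use the device at least daily for 30 minutes", and the diary runs alongside: "Participants were prompted to record analgesic use, pain, and device use daily for a month on the web-based platform". No run-in or pre-device diary is described.

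The Participant Timeline also schedules "Dose, Opioid formulation, number Source (DOSE tool), other analgesics" at the initial visit for both strata. Nothing makes that record the baseline for the primary.

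**The concern.** The primary objective is whether M-Stim reduces opioids by 30% compared with TENS. A baseline for that question has to come before the device can act. Here it consists of two weeks of device use after randomisation, so the outcome answers a different question: how much MME changes from the first fortnight on the device to the second.

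A participant who cuts opioids at once and stays at the lower level shows no change. One whose equal reduction starts on day 15 shows all of it. The outcome can therefore miss a real difference between devices, and can favour the slower one. If both devices lower MME by 30%, M-Stim from day 1 and TENS from day 15, the rule scores M-Stim 0% and TENS 30%.

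Comparing the changes between arms, or adjusting for days 1-14, does not repair this, because the early difference between devices sits inside the value being subtracted or adjusted for.

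**Working it through.** **Inputs from the documents.** Windows of days 1-14 and 15-28 (Outcomes, Participant Timeline). From Sample Size: reductions of 26.2 (SD 32.8) and 5.8 (SD 34.2) MME, 50 per group, two-sided 0.05, stated power 85.4%.

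**Assumed, because the documents do not give them.** The onset profile of the MME effect, and the SD of the change between fortnights.

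**1. The plan's own figure.** Difference = 26.2 − 5.8 = 20.4. Pooled SD = √((32.8² + 34.2²)/2) = 33.5. d = 20.4/33.5 = 0.609. A two-sample t-test with 50 per group has 85.4% power, which matches. The borrowed effect is a reduction after stimulator implantation versus conventional treatment, not a change between two early on-treatment fortnights. The figure is also a between-arm power, whereas Statistical Methods names a paired test for this contrast.

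**2. Share of the effect the outcome keeps.** Let e(t) be the fraction of the full effect present on day t. Kept share = mean of e over days 15-28 minus mean of e over days 1-14.

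| Onset (assumed) | Mean e, days 1-14 | Mean e, days 15-28 | Kept | Of 20.4 MME |
|---|---|---|---|---|
| Complete on day 1 | 1.00 | 1.00 | 0% | 0 |
| Linear to full by day 3 | 0.93 | 1.00 | 7% | 1.5 |
| Linear to full by day 7 | 0.79 | 1.00 | 21% | 4.4 |
| Linear to full by day 14 | 0.54 | 1.00 | 46% | 9.5 |
| Step on day 8 | 0.50 | 1.00 | 50% | 10.2 |
| Linear to full by day 28 | 0.27 | 0.77 | 50% | 10.2 |
| Step on day 15 | 0 | 1.00 | 100% | 20.4 |

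**3. What a true 30% reduction scores.** Score = 1 − (mean MME, days 15-28)/(mean MME, days 1-14), with the pre-device level set to 1.
- Step on day 1: 1 − 0.70/0.70 = 0%.
- Step on day 8: 1 − 0.70/0.85 = 17.6%.
- Step on day 15: 1 − 0.70/1.00 = 30%.

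**4. Illustrative power of a between-arm comparison of the changes.** Same t-test, with d = 0.609 × kept share ÷ SD multiplier.

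| Kept | SD × 1 (33.5) | SD × 0.75 | SD × 0.5 |
|---|---|---|---|
| 0% | 5% | 5% | 5% |
| 21% | 10% | 14% | 25% |
| 46% | 29% | 46% | 80% |
| 50% | 33% | 52% | 85% |

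With 0% kept, the expected difference is zero and power equals alpha whatever the SD.

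**5. Like-for-like for slow onset.** With a linear rise to day 28, a between-arm comparison of days 15-28 itself sees only 77% of the full effect, giving 64% power at SD 33.5. The cost of the two-window rule in that case is 64% to 33%, not 85% to 33%.

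**The case against.** **The choice is explained.** Protocol Amendments says the investigators had no access to prescribing records and that opioid reduction was itself a desired outcome. This shows a disclosed compromise. It does not address an early effect, and neither reason requires an on-treatment baseline.

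**Other planned analyses could show a fast effect.** As worded, the between-arm relative risks for MME and use days in Statistical Methods subtract nothing for days 1-14. That is true and should be acknowledged. They are not the stated prior-use primary, and no adjustment for pre-device use is described.

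**The size is uncertain.** This stands. The onset profiles are assumptions, and the change between adjacent fortnights in one person may vary less than 33.5. Half that SD would bring power at 50% capture back to 85%.

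Three stronger readings are tempting, and the documents do not support them.
- A reader might infer that any reduction beginning in the first two weeks is lost. Only an effect complete on day 1 is lost entirely; one starting on day 8 keeps half.
- A reader might infer that the plan itself expects a rapid opioid effect, from the NRS after 30 minutes and the 10-day acute outcome. Both are pain scores. Acute participants are by definition not using opioids for the current exacerbation, and the chronic pain primary is at 6 months.
- A reader might infer a definite fall in power from 85% to 33%. That rests on a borrowed SD and, for slow onset, on the wrong comparator.

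**Conclusion.** The concern holds. It follows from the visit schedule and the outcome definition alone that both windows are on treatment, and that the part of the effect present in days 1-14 is subtracted. The loss runs from all of an effect complete on day 1 to none of one that starts on day 15. The paired t-test shares the flaw, as would a between-arm comparison of the changes.

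Confidence is high for this design fact and low for its size in this trial. The power figures (about 10% to 25% at 21% capture, about 33% to 85% at 50% capture, with 50 per group) are illustrations under assumed onset and an SD of 1 to 0.5 times 33.5. The correction is still needed, because a primary outcome that can score zero for a fast, lasting effect can give a wrong answer to the stated objective.

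**What to change.** - **Contrast.** Make the prior-use primary the M-Stim versus TENS difference in MME over diary days 15-28 (or all 28 days), among participants whose prior or ongoing use was recorded at entry. The 28-day version counts early onset but dilutes late onset: a step on day 15 keeps (0 + 1)/2 = 50%.
- **Baseline.** Adjust for initial-visit DOSE MME if its recall window yields a usable MME per day. The documents do not state that window. Otherwise compare the arms unadjusted, which randomisation keeps valid.
- **Days 1-14.** Do not use them as baseline or covariate. Report them as an early-effect outcome.
- **Later time points.** Report the same contrast at month 3, and at month 6 for the chronic stratum only, since acute participants are followed for 3 months.
- **Transparency.** Protocol Amendments shows that registration data were examined after enrolment was complete. If outcome data have also been examined, report the new contrast beside the two-window one and label it as a later change.

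The data are already scheduled, so the work is in the outcome and analysis wording. The costs are a noisier or absent baseline covariate, with a loss of precision that the documents do not allow us to size, and having to disclose a late change to a primary outcome.
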